7.5 Covariates and Prognostic Factors

In the efficacy analysis, the stratification factors and baseline values will be used as covariates in the analysis of all the primary, secondary, and exploratory endpoints.

7.6 Subgroups

As several factors are considered to be related to treatment, subgroup analyses will be performed to evaluate whether the treatment effects are consistent across different subgroups. These factors include:

- Symptom duration >=12 weeks and <= 24 weeks
- Symptom duration > 24 weeks

Additional exploratory subgroup analysis may be conducted using the baseline clinical characteristics (such as COVID-19 vaccination status) and laboratory parameters.

7.7 Standard Calculations

7.7.1 Age

Age will be calculated as the number of completed years between the date of informed consent and the subject's birth date.

7.7.2 Body Mass Index (BMI)

BMI will be calculated using height (in cm) and weight (in kg) according to the formula noted below.

BMI
$$(kg/m^2)$$
 = weight $(kg) / [[height (cm)/100]^2]$

7.7.3 Change from Baseline

For any of the effectiveness measurements change from baseline will be calculated using the formula noted below.

Change from baseline =

Post Baseline Measurement – Baseline Measurement

7.7.4 Censoring rule for subjects with outcome of Death

For analyses of duration of hospitalization, all deaths within 56 days will be considered censored at Day 56. Conceptually, a death corresponds to an infinite length of stay support but censoring at any time greater than or equal to Day 56 gives the same answer as censoring at Day 56; both correspond to giving deaths the worst rank.

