7.3 Handling of Missing Data

Every effort will be made to obtain required data at each scheduled evaluation from all subjects who have been randomized to minimize missing data. Missing data will not be imputed.

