8.2.2 Secondary Efficacy Endpoint

8.2.2.1 Duration of COVID-19 associated symptoms from start of study treatment (Day 0) based on self-assessment using daily symptom diary.

Duration is defined as number of days when any symptoms scored as

- 2 or 3 at baseline are still scored as 2 or 3 (i.e., not 0 or 1) through Day 56, or
- 1 or 0 at study entry are scored as 1 or worse (i.e., not 0) through Day 56.

The duration (days) of COVID-19 associated symptoms will be compared between the treatment groups using the a non-parametric method or a rank-ANCOVA analysis i.e., an ANCOVA analysis on rank-transformed data.

8.2.2.2 Number of symptom-free days of COVID-19 associated symptoms that were present at the start of study treatment (Day 0) based on self-assessment using daily symptom diary.

Symptom-free days are defined as number of days when any symptoms scored as 1, 2 or 3 at baseline are still scored as 0 through Day 56.

The number of symptom-free days of COVID-19 associated symptoms will be compared between the treatment groups. Similar analysis methods used for the section 8.2.2.1 will be applied to analyze the data from this endpoint.

8.2.2.3 Progression (or worsening) of COVID-19-associated symptoms through Day 56 compared to baseline.

Progression or symptom worsening is defined as number of days when any symptoms scored as

- 2 at baseline are still scored as 3 through Day 56, or
- 1 at baseline are still scored as 2 or 3 through Day 56, or
- 0 at study entry are scored as worse (i.e., not 0) through Day 56.

The progression (or worsening) of COVID-19-associated symptoms will be compared between the

treatment groups. Similar analysis methods used for section 8.2.2.1 will be applied to analyze the data from this endpoint.

8.2.2.4 Change from baseline in PROMIS® Fatigue Score at Days 28 and 56.

The change from baseline in PROMIS® Fatigue Score will be compared between the treatment groups will be presented and summarized descriptively by treatment group using ANCOVA adjusting for stratification factors. If the data is not normally distributed, a non-parametric method or a rank-ANCOVA analysis i.e., an ANCOVA analysis on rank-transformed data will be used.

8.2.2.5 Change from baseline in PROMIS® Cognitive Function Score at Days 28 and 56.

The change from baseline in PROMIS® Cognitive Score will be compared between the treatment groups. Similar analysis methods used for section 8.2.2.4 will be applied to analyze the data from this endpoint.

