8.2.2.8 Duration (days) of hospitalization during the treatment phase

The duration of hospitalization will be compared between the treatment groups. Similar analysis methods used for section 8.2.2.1 will be applied to analyze the data from this endpoint.

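### SAP 7.7.4 gives deaths the worst rank for hospitalization days only; symptom duration and progression days have no death rule, so an early death can rank among the best outcomes

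*Combined protocol and SAP*

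**What the plan says.** SAP 7.7.4 is the only death rule in the SAP's data conventions, and its scope is stated: "For analyses of duration of hospitalization, all deaths within 56 days will be considered censored at Day 56". It compares a death to an infinite stay and concludes that censoring at Day 56 and censoring at any later time "both correspond to giving deaths the worst rank".

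SAP 8.2.2.8 then analyses duration of hospitalization by reference: "Similar analysis methods used for section 8.2.2.1 will be applied to analyze the data from this endpoint". The method in 8.2.2.1 is "a non-parametric method or a rank-ANCOVA analysis i.e., an ANCOVA analysis on rank-transformed data".

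The symptom endpoints use the same method. For 8.2.2.1, "Duration is defined as number of days when any symptoms scored as" 2 or 3 at baseline stay at 2 or 3, or those scored 0 or 1 at entry are scored 1 or worse. For 8.2.2.3, "Progression or symptom worsening is defined as number of days when any symptoms scored as" worse than at baseline. Both run through Day 56, and fewer days is better. Symptom-free days (8.2.2.2) is also a count through Day 56, but there more is better.

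On missing values, SAP 7.3 says "Missing data will not be imputed". Protocol 8.9.3 prescribes multiple imputation for efficacy data instead. Neither section says what to do with diary days after a death.

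**The concern.** There are two separate matters.

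The first is wording. Censoring belongs to a time-to-event analysis, where a death censored at the end of follow-up never reaches discharge and so ranks last. Rank-ANCOVA takes a number for each subject and nothing else. The word in 7.7.4 therefore has nothing to attach to in the named method, and the programmer has to turn it into a value.

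The second is substantive. On symptom duration and progression days a subject scores only for days on which bad symptoms are recorded. A subject who dies records no more of them. With no death rule and no imputation, the count stops at death and a low count is a good result. An early death would then count in favour of the arm in which it occurred, contrary to the principle the SAP adopts for hospitalization.

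**Working it through.** The plan gives no figure that depends on this point: the 50 subjects in SAP 4 rest on clinical judgment. What can be checked is the stated property, that deaths rank worst.

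**Formula.** Mid-rank of a value = (number of smaller values) + (number of equal values, itself included, + 1)/2, among 50 subjects of whom one dies. Rank 1 is the fewest days.

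**Hospitalization days.** Illustrative survivors: 46 with 0 days, and one each with 2, 5 and 9.
- Death entered as 56: 49 + (1 + 1)/2 = 50, the worst rank.
- If the 9-day survivor instead has 56 days: 48 + (2 + 1)/2 = 49.5, tied worst.
- If that survivor instead has 57 days: 48 + (1 + 1)/2 = 49. This is possible in principle, because the endpoint covers the treatment phase, and eight intervals of 7 ± 1 days span 8 × 6 = 48 to 8 × 8 = 64 days.

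So the intent of 7.7.4 is met by the value 56, apart from that remote case. A value above any possible count would meet it without exception.

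**Symptom duration with no death rule.** Take a patient symptomatic every day until death on Day d, entered with d days. This is the highest count such a patient can reach, so it is the case least favourable to the concern.

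A fixed example first: 49 survivors with 8, 9, …, 56 days and a death with 5 days. The death ranks 0 + (1 + 1)/2 = 1, the best of 50. Entered as 56, it ranks 48 + (2 + 1)/2 = 49.5.

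The documents give no distribution of symptom days, so three were assumed. Each survivor's count is binomial(56, p), with p drawn from a Beta distribution, in 4,000 simulations per cell:
- high persistence: Beta(4, 1.5), mean 56 × 4/5.5 = 40.7 days
- middle: Beta(2, 2), mean 56 × 2/4 = 28 days
- low: Beta(1.2, 3), mean 56 × 1.2/4.2 = 16 days

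Mean rank of the death (1 = best of 50):

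| Day of death | High | Middle | Low |
|---|---|---|---|
| 3 | 1.0 | 1.7 | 6.8 |
| 7 | 1.1 | 3.6 | 14.0 |
| 14 | 1.6 | 9.1 | 25.7 |
| 28 | 7.3 | 25.5 | 41.8 |
| 42 | 24.7 | 41.9 | 48.7 |

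Entering the death as 56 days moves the mean rank to between 49.5 and 50.0 throughout.

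**Progression days.** The count is likewise capped at days alive. The same mechanism applies, to a degree that depends on how many worsening days survivors have.

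**Symptom-free days.** With 49 survivors spread evenly from 0 to 56 days and a death with 0 days, the death ranks 0 + (2 + 1)/2 = 1.5 of 50 counted from the fewest, which here is the worst end. Death already ranks poorly.

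**How often it could arise.** The documents give no expected mortality. The chance of at least one death in 50 is 1 − (1 − p)^50. For assumed risks p of 0.1%, 0.5%, 1% and 2% it is 4.9%, 22%, 39% and 64%.

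**The case against.** The strongest reply concerns hospitalization. A reader might infer that the planned analysis leaves deaths at their observed stay. With survivors at 4, 6 and 9 days, a death after 3 hospital days would then rank 46 + (1 + 1)/2 = 47, ahead of all three. A death outside hospital would rank 0 + (47 + 1)/2 = 24, tied with everyone never admitted. The documents do not support this. SAP 7.7.4 covers all deaths within 56 days, in or out of hospital, and states the result it wants. An analyst following it would enter 56 and rank the death last or tied last. Those ranks arise only if 7.7.4 is ignored. The non-parametric option in 8.2.2.1 is also unnamed, so a test that handles censoring is not strictly excluded. This part of the objection stands.

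On the symptom counts the objection stands only in part. Symptom-free days run the other way, and a late death need not rank well. An analyst might also treat an incomplete count as missing altogether; the death would then drop out of the comparison, which is not the worst rank either. If the protocol's multiple imputation governed, days after death would be filled in as if the patient were alive, and that is not a death rule.

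Giving death the worst rank on a diary endpoint is a choice of estimand, and a while-alive approach is another legitimate one. The SAP has to state one. Worst rank is the choice it has already made for hospitalization.

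Dropout is plausibly commoner than death in this population, and it cuts the count short in the same way. That is correct, and it widens the repair.

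**Conclusion.** The point holds in two unequal parts. For duration of hospitalization, the term censoring does not fit rank-ANCOVA, but the intent is clear and the value 56 delivers it, so this is a matter of wording. For symptom duration and progression days there is a real gap: no death rule applies, and with no imputation an early death gives a low, favourable count. For symptom duration, a Day 7 death ranks on average 1.1 to 14.0 of 50 under the assumed distributions.

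A reader might go further and infer that death ranks well on every day count. It does not: the hospitalization rule prevents it there, symptom-free days already penalise death, and by Day 28 the mean rank on symptom duration ranges from 7.3 to 41.8.

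The ranks rest on assumed symptom distributions, and on reading 7.3 to mean that unrecorded days add nothing to the count. The expected effect on the trial is small: these are secondary endpoints in an exploratory trial of 50, and deaths should be rare. It is still worth correcting, because the plan as written would get the result wrong if an early death occurred.

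**What to change.** Replace the text of SAP 7.7.4, deleting the reference to censoring, with:

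*In the rank analyses of hospitalization days, symptom duration and progression days, any death by Day 56, in or out of hospital, is assigned a value above the largest possible count. For symptom-free days it is assigned a value below the smallest.*

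In the same revision, state how counts are formed when a diary ends early through dropout, and reconcile SAP 7.3 (no imputation) with protocol 8.9.3 (multiple imputation). Otherwise early dropouts keep the same favourable counts.

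The cost is one SAP paragraph plus the missing-data reconciliation, made before database lock and unblinding. Sample size, alpha and data collection do not change. The downside is that death is merged into the symptom endpoints, so deaths should also be reported separately by arm.

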8. STATISTICAL METHODS

All data collected during this study will be presented in subject data listings. All statistical analyses will be performed using SAS® for Windows, version 9.4 or later.

8.1 Summarizing and Tabulating the Collected Data

All data collected will be summarized according to the variable type:

- Continuous data summaries will include number of observations, mean, standard deviation, median, and minimum and maximum values.
- Categorical data summaries will include frequency counts and percentages.

8.1.1 Subject Disposition and Withdrawals

The disposition of all subjects who sign an ICF will be provided. The number of subjects screened, screen failure, randomized, received at least one treatment, completed, and discontinued during the study, as well as the reasons for all discontinuations will be summarized by treatment group. Disposition and reason for study discontinuation will also be provided as a by-subject listing.

8.1.2 Protocol Deviations

Protocol deviations will be identified and classified as minor or major before un-blinding.

Protocol deviations for all randomized subjects will be listed as by-subject listing and major deviations will be summarized descriptively according to the following categories:

- Did not meet Inclusion/Exclusion criteria but entered into study
- Developed withdrawal criteria during the study but not withdrawn
- Received excluded concomitant medication
- Study treatment dosing deviation

8.1.3 Demographics and Baseline Characteristics

Demographics and baseline characteristics (i.e., Age, Race, Gender, Tobacco use history etc.) will be summarized using appropriate descriptive statistics.

Medical history of the subjects will be provided as a by-subject listing.

8.1.4 Prior and Concomitant Medications

Prior and concomitant medications will be summarized for the Safety population. All prior and concomitant medications recorded in the eCRFs will be coded to generic term and all matching Anatomic Therapeutic Classification (ATC) codes using the most recent version of the WHO Drug WHO Drug Dictionary. Summaries will be prepared using the coded terms. All prior and concomitant medications recorded in the eCRFs will also be listed.

8.1.5 Treatment Exposure

All data from administration of study drug will be presented.

In addition, extent of exposure will be summarized using total number of injections received during the treatment phase for all subjects, including n, median, mean, SD, min, max. The duration (days) of exposure from the treatment start date to the treatment end date will be summarized.

8.2 Analysis of Efficacy Data

The primary analysis will be conducted on the mITT population. The PP population will be used as the supportive analysis population for analysis of the primary and secondary efficacy endpoints.

8.2.1 Primary Efficacy Endpoint

The primary endpoint for the study is changes from baseline in daily COVID-19-related symptom severity score through day 56.

Daily COVID-19 related symptom score is the sum of score from Assessment of COVID-19-related symptoms.

For this endpoint, proportions of subjects in each category will be summarized and compared using proportional odds model, adjusting for baseline COVID-19 related symptom score and stratification factors. Odds Ratio estimates and 95% Confidence Interval will also be calculated.

8.2.2 Secondary Efficacy Endpoint

8.2.2.1 Duration of COVID-19 associated symptoms from start of study treatment (Day 0) based on self-assessment using daily symptom diary.

Duration is defined as number of days when any symptoms scored as

- 2 or 3 at baseline are still scored as 2 or 3 (i.e., not 0 or 1) through Day 56, or
- 1 or 0 at study entry are scored as 1 or worse (i.e., not 0) through Day 56.

The duration (days) of COVID-19 associated symptoms will be compared between the treatment groups using the a non-parametric method or a rank-ANCOVA analysis i.e., an ANCOVA analysis on rank-transformed data.

8.2.2.2 Number of symptom-free days of COVID-19 associated symptoms that were present at the start of study treatment (Day 0) based on self-assessment using daily symptom diary.

Symptom-free days are defined as number of days when any symptoms scored as 1, 2 or 3 at baseline are still scored as 0 through Day 56.

The number of symptom-free days of COVID-19 associated symptoms will be compared between the treatment groups. Similar analysis methods used for the section 8.2.2.1 will be applied to analyze the data from this endpoint.

8.2.2.3 Progression (or worsening) of COVID-19-associated symptoms through Day 56 compared to baseline.

Progression or symptom worsening is defined as number of days when any symptoms scored as

- 2 at baseline are still scored as 3 through Day 56, or
- 1 at baseline are still scored as 2 or 3 through Day 56, or
- 0 at study entry are scored as worse (i.e., not 0) through Day 56.

The progression (or worsening) of COVID-19-associated symptoms will be compared between the

treatment groups. Similar analysis methods used for section 8.2.2.1 will be applied to analyze the data from this endpoint.

8.2.2.4 Change from baseline in PROMIS® Fatigue Score at Days 28 and 56.

The change from baseline in PROMIS® Fatigue Score will be compared between the treatment groups will be presented and summarized descriptively by treatment group using ANCOVA adjusting for stratification factors. If the data is not normally distributed, a non-parametric method or a rank-ANCOVA analysis i.e., an ANCOVA analysis on rank-transformed data will be used.

8.2.2.5 Change from baseline in PROMIS® Cognitive Function Score at Days 28 and 56.

The change from baseline in PROMIS® Cognitive Score will be compared between the treatment groups. Similar analysis methods used for section 8.2.2.4 will be applied to analyze the data from this endpoint.

8.2.2.6 Change from baseline in PROMIS® Sleep Disturbance Score at Days 28 and 56.

The change from baseline in PROMIS® Sleep Score will be compared between the treatment groups.. Similar analysis methods used for section 8.2.2.4 will be applied to analyze the data from this endpoint.

8.2.2.7 *Incidence of hospitalization during the treatment phase*

The Incidence of hospitalization will be compared between the treatment groups. Similar analysis methods used for section 8.2.2.1 will be applied to analyze the data from this endpoint.

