7.16. PROMIS® FATIGUE SCALE

This score is based on questions focused on physical fatigue and psychological fatigue. The assessment will be performed (self-administered by the subject) at V2, V4, V6, V8, V10, V12, V14, V16, and V17 (EOT). See Appendix 3.

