8.9.3. Missing Data

Every effort will be made to obtain required data at each scheduled evaluation from all subjects who have been randomized to minimize missing data. However, in the event when there is missing data the following imputation methods will be used.

For efficacy evaluations, multiple imputation methods will be used to handle missing data. This imputation method is a robust method to impute missing measurements. The imputation will be carried out in SAS version 9.4 or later using PROC MI. Each imputation model will include the stratification factor as a covariate in the model. The details of multiple imputation will be included in the statistical analysis plan.

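### PROMIS scores are collected at eight post-baseline visits but compared by ANCOVA at Days 28 and 56 only, without imputation, so early leavers drop out of the Day 56 estimate despite having earlier scores.

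*Combined protocol and SAP*

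**What the plan says.** Protocol 7.16 has the fatigue scale self-administered "at V2, V4, V6, V8, V10, V12, V14, V16, and V17 (EOT"; 7.17 and 7.18 give the same visits for cognitive function and sleep disturbance. That is a baseline and eight post-baseline scores per scale.

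The endpoint in the SAP is "8.2.2.4 Change from baseline in PROMIS® Fatigue Score at Days 28 and 56". Arms are compared "using ANCOVA adjusting for stratification factors", and SAP 7.5 adds the baseline value: "the stratification factors and baseline values will be used as covariates". If the data are not normal, the SAP moves to a non-parametric or rank-ANCOVA analysis; it gives no criterion for that decision. For cognition and sleep, SAP 8.2.2.5 and 8.2.2.6 say "Similar analysis methods used for section 8.2.2.4 will be applied to analyze the data from this endpoint". No repeated-measures model is named.

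On missing values the two documents disagree. SAP 7.3: "Missing data will not be imputed". Protocol 8.9.3: "For efficacy evaluations, multiple imputation methods will be used to handle missing data", followed by "The details of multiple imputation will be included in the statistical analysis plan". The SAP contains no such details.

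**The concern.** The mITT population takes in everyone who received a dose, but an ANCOVA on change at Day 56 can use only subjects with a Day 56 value. Someone who leaves after the Day 49 visit with seven post-baseline scores is in the population and absent from the estimate.

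Dropout is foreseen: protocol 5.3 provides for voluntary withdrawal and for withdrawal from the study after two consecutive missed doses. If who leaves depends on how they were scoring, and that selection differs between arms, those who remain are no longer comparable. The intermediate scores needed to correct this under a missing-at-random assumption are collected, but no comparison of the arms uses them. At stake are the Day 56 contrasts of three secondary endpoints, each tested at 0.05.

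**Working it through.** The plan states no power, effect size, SD or dropout rate, so there is no figure of its own to reproduce.

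**Inputs from the documents:** 50 subjects, 1:1, so 25 per arm (SAP 4); the visit schedule (protocol 7.16-7.18); ANCOVA with stratum and baseline (SAP 7.5, 8.2.2.4); no imputation (SAP 7.3).

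**Assumed, because the documents are silent:** dropout rates, visit correlations, the dropout mechanism, and a 0.50 SD effect where one is used.

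**1. Visits.** V4, V6, V8, V10, V12, V14, V16 and V17 are Days 7, 14, 21, 28, 35, 42, 49 and 56: eight. Days 28 and 56 are tested: two. 8 - 2 = 6, and 6/8 = 75% of post-baseline assessments enter no comparison of the arms.

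**2. Precision at Day 56.** With n completers per arm and baseline correlation r, the ANCOVA standard error in SD units is √[2(1 - r²)/n]. For r = 0.7 at all visits:
- No dropout: √(2 × 0.51/25) = 0.202. MMRM gives the same.
- 20% dropout: √(2 × 0.51/20) = 0.226. MMRM gives 0.219, a variance ratio of (0.2192/0.2258)² = 0.942.

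With compound symmetry at 0.5-0.8 or AR(1) at 0.7-0.9, the gain in effective sample size at Day 56 is 0% with complete data, 1.4-3.8% at 10% dropout, 3.1-8.2% at 20% and 5.2-13.6% at 30%. These figures treat the covariance as known. In simulation at 25 per arm, the Day 56 variance moved by no more than about 6% in either direction.

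**3. Bias with no true effect.** Simulation with 60,000 per arm; compound symmetry 0.5 and 0.7, AR(1) 0.8 and 0.9. Where dropout is score-related, its log-odds change by 1 per SD of the last observed score. Absolute bias of the observed-case ANCOVA at Day 56, in SD:

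| Dropout per arm | Score-related in one arm only | Opposite directions in the two arms | Same in both arms |
|---|---|---|---|
| 10% | 0.02-0.05 | 0.04-0.08 | about 0 |
| 20% | 0.04-0.09 | 0.09-0.17 | about 0 |
| 30% | 0.07-0.13 | 0.14-0.25 | about 0 |

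An estimate that also uses the earlier visits is within about 0.01 SD of zero in every cell.

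**4. Bias with a true effect of 0.50 SD and dropout linked to poor response.** The effect itself makes the selection differ between arms. Estimates at Day 56:

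| Setting | Observed-case ANCOVA | All visits |
|---|---|---|
| 25 per arm, 16-26% dropout, moderate link | 0.47-0.48 | 0.49-0.51 |
| 25 per arm, 25-35% dropout, strong link | 0.42-0.44 | 0.49-0.51 |
| 25 per arm, second simulation, moderate link | 0.49-0.50 | 0.49-0.50 |
| 25 per arm, second simulation, strong link | 0.46-0.47 | 0.49-0.50 |
| 100,000 per arm, 18-29% dropout, strong link | 0.45-0.47 | 0.50-0.51 |

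The shortfall runs from about 0.50 - 0.49 = 0.01 to 0.50 - 0.42 = 0.08 SD, towards no effect.

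**5. Bias against the standard error.** With r = 0.65 and 18-21 completers per arm, the standard error is √[2(1 - 0.4225)/21] = 0.23 to √[2(1 - 0.4225)/18] = 0.25. A bias of 0.08 is about a third of that. The worst 20% cell in step 3 (AR(1) 0.9) is 0.168/0.285 = 0.59 of its standard error.

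**The case against.** Baseline-adjusted ANCOVA at pre-specified days is an accepted analysis, and protocol 8.10.4 itself names it for continuous secondary endpoints. The trial is exploratory and unpowered. The bias is mostly a fraction of a standard error. Multiple imputation using the intermediate visits would serve as well as MMRM and would honour protocol 8.9.3. All of that stands. It limits the weight of the point and means that the protocol wording must be dealt with too.

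A reader might infer four stronger things that the documents and figures do not support:
- **That six visits are thrown away.** SAP 8.1 summarises, and SAP 8 lists, all collected data. The visits are absent from the comparison of arms, not from the report.
- **That MMRM buys precision.** At Day 56 it hardly does (step 2). An average over Days 7-56 would have 41-47% of the variance of a single-visit contrast, but that average is not an endpoint in either document.
- **That any loss of poor responders biases the result.** With no effect and the same mechanism in both arms the bias is about zero.
- **That MMRM cures dropout.** The simulated mechanisms are missing at random by construction, which favours a likelihood model. Nothing here shows protection when dropout depends on unobserved scores.

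Protocol 4.2.4 treats the last treatment-phase visit as end of treatment, so it might be thought that a leaver's last score stands in for Day 56. The SAP has no rule that maps an early visit to Day 56.

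**Conclusion.** The point holds as a dropout problem. The plan has no missing-at-random handling for the PROMIS endpoints at Day 56, although the scores for it are collected and the protocol promised it. Under assumed dropout of about 16-35% linked to earlier scores, the bias is roughly 0.01-0.08 SD of an assumed 0.50 SD effect. With opposite mechanisms in the two arms it reaches about 0.17 SD at 20% dropout, and more at 30%. It vanishes with no effect and a common mechanism. Reading the plan as separate ANCOVAs is an inference, but with two named days and no visit term no other plain reading is left. These are secondary endpoints of an exploratory trial, so the change is worth making because it is cheap, not because the trial fails without it.

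**What to change.** In SAP 8.2.2.4 to 8.2.2.6, pre-specify one MMRM per scale on all eight post-baseline visits:
- **Terms:** arm, visit, arm-by-visit, baseline, baseline-by-visit and symptom-duration stratum.
- **Covariance:** unstructured, with Kenward-Roger degrees of freedom. Eight visits need 8 × 9/2 = 36 covariance parameters from 50 subjects, so state a fallback order, for example heterogeneous Toeplitz, then AR(1).
- **Reporting:** the Day 28 and Day 56 contrasts, as the unchanged endpoints.
- **Sensitivity:** keep ANCOVA or rank-ANCOVA as a named sensitivity analysis instead of a switch after a normality check, and add one missing-not-at-random analysis.

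Reconcile SAP 7.3 with protocol 8.9.3. MMRM itself needs no imputation, but a missing-not-at-random analysis may, so SAP 7.3 should say what is allowed. Align protocol 8.10.4, or record the departure from its ANCOVA in the SAP before unblinding.

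Cost: SAP wording, slightly more programming, a documented departure from the protocol's ANCOVA, and possible non-convergence at this sample size, which the fallback order covers. No new data or visits are needed.

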7.14. CLINICAL SYMPTOM SCORE

Clinical symptom score will be assessed at Screening (V1) and baseline (V2) based on following commonly reported symptoms consistent with COVID-19 infection for a prolonged period of time (>12 weeks):

- Respiratory symptoms such as cough, sore throat, stuffy or runny nose, shortness of breath (difficulty breathing), tightness of chest etc.
- Neurological symptoms such as difficulty in concentration (brain fog), sleep disturbance/insomnia, headache, dizziness, anxiety, tingling or numbness, loss of sense of smell or taste.
- Cardiovascular and Gastrointestinal symptoms such as feeling of fast heartbeat, nausea, vomiting, diarrhea.

CONFIDENTIAL Page 66 of 101

- Musculoskeletal symptoms such as muscle aches/cramps, muscle weakness, joint pain/swelling.
- General immune response symptoms such as fatigue (low energy or tirednesschills or shivering, feeling hot or feverish or exertional malaise (feeling of discomfort, illness, or lack of well-being after physical activity or mental stress).

Note: Clinical Symptom Score is obtained from the patient diary (refer to Appendix 1 for scoring instructions).

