7. DATA CONVENTION AND RELATED DEFINITIONS

7.1 Baseline Definition

For all parameters, baseline will be defined as the last available value before the randomized treatment.

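### The secondary-endpoint sections of the SAP omit the baseline covariate that SAP 7.5 requires, and 8.2.2.1 leaves the method open, so a less precise analysis is permitted

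*Combined protocol and SAP*

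**What the plan says.** SAP 7.5 sets a general rule: "the stratification factors and baseline values will be used as covariates in the analysis of all the primary, secondary, and exploratory endpoints". SAP 7.1 adds that "baseline will be defined as the last available value before the randomized treatment".

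The endpoint sections follow that rule unevenly:

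- **Primary (8.2.1).** Both covariates are named: "adjusting for baseline COVID-19 related symptom score and stratification factors".
- **PROMIS Fatigue (8.2.2.4).** The comparison is made "using ANCOVA adjusting for stratification factors". The fallback names no covariate: "If the data is not normally distributed, a non-parametric method or a rank-ANCOVA analysis". Sections 8.2.2.5 (cognition) and 8.2.2.6 (sleep) take over this method, as do seven of the eight items in 8.2.3.
- **Symptom duration (8.2.2.1).** Groups are compared "using the a non-parametric method or a rank-ANCOVA analysis". No covariate is named and no rule for choosing is given. Symptom-free days (8.2.2.2), worsening days (8.2.2.3), and hospitalization incidence and duration (8.2.2.7, 8.2.2.8) refer back to this section.

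Protocol 8.9.2 leaves the choice of covariates to the SAP, so the SAP is where this has to be settled.

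**The concern.** An analyst who programs from the endpoint sections could fit the PROMIS change scores on treatment and stratum alone. The same analyst could compare the day counts with a two-sample rank test that uses neither baseline nor the randomization stratum. An analyst who works from 7.5 would do neither. The SAP does not say which text prevails. Because 8.2.1 lists baseline explicitly, its absence from 8.2.2.4 could be taken as deliberate.

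Two things are at stake. One is precision, in a trial of 50 subjects sized without a power calculation (SAP 4). The other is an avoidable choice of model: SAP 7.4 tests every effectiveness endpoint at 0.05 without multiplicity adjustment, and a choice not fixed in the SAP could be made after unblinding.

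**Working it through.** **Step 1: set the endpoint sections against 7.5.** There are eight secondary endpoints.

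| Endpoints | Covariates named in the section | Baseline available? |
|---|---|---|
| 3 PROMIS scores (8.2.2.4 to 8.2.2.6) | Stratum | Yes: measured at V2 before dosing (Protocol 7.16 to 7.18; Table 4-2, note 8) |
| 3 symptom day counts (8.2.2.1 to 8.2.2.3) | None | No baseline day count, but the symptom score is assessed at V2 (Protocol 7.14) |
| 2 hospitalization endpoints (8.2.2.7, 8.2.2.8) | None | No counterpart |

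So 3 + 3 + 2 = 8: in no section does the text match 7.5. In the exploratory set, the Global Health Assessment is collected only at V17 (Protocol 7.19), yet SAP 8.2.3 analyses its change from baseline. That analysis cannot be carried out.

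**Step 2: size for the PROMIS change scores.** The plan has no figure to reproduce: it gives no SD, effect size or correlation. Inputs from the documents are 25 per arm (50 at 1:1) and alpha 0.05. Two-sided testing, equal variances s² at baseline and follow-up, and r are assumptions.

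- Error variance of change without baseline: 2s²(1 − r).
- Error variance with baseline as covariate: s²(1 − r²).
- Ratio: (1 − r²) / [2(1 − r)] = (1 + r)/2.
- Difference detectable with 80% power: (1.960 + 0.842) × √(2/25) × residual SD = 0.792 × residual SD.

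Detectable differences are in units of s. Power is for a true effect of 0.6 s.

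| r | Variance ratio | Detectable difference, without → with baseline | Power, without → with baseline |
|---|---|---|---|
| 0.3 | 0.65 | 0.938 → 0.756 | 43% → 60% |
| 0.5 | 0.75 | 0.792 → 0.686 | 56% → 69% |
| 0.7 | 0.85 | 0.614 → 0.566 | 78% → 84% |
| 0.8 | 0.90 | 0.501 → 0.475 | 92% → 94% |

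A simulation of 4,000 trials per setting at the same effect, with the stratum in both models, gave 42% → 58%, 55% → 66% and 76% → 82% for r = 0.3, 0.5 and 0.7. The two models disagreed on p < 0.05 in about 25%, 18% and 10% of trials.

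**Step 3: chance imbalance.** One standard error of the baseline difference between arms is √(2/25) = 0.283 s. Given an imbalance of that size, the estimate without baseline shifts by (1 − r) × 0.283 s: 0.7 × 0.283 = 0.198 s at r = 0.3, and 0.2 × 0.283 = 0.057 s at r = 0.8.

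**Step 4: symptom day counts.** A covariate with correlation r to the (ranked) count leaves 1 − r² of the variance. For r = 0.4 this is 1 − 0.16 = 0.84, a 16% cut. For r = 0.7 it is 1 − 0.49 = 0.51, a 49% cut. This r is also assumed, and no day-count endpoint was simulated.

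**The case against.** The strongest reply is that 7.5 already governs. Section 8.2.2.4 does not say that the strata are the only covariates, so reading it as incomplete satisfies both sections. The label ANCOVA also points that way, since a model with only a two-level stratum would be a two-way ANOVA. This stands in part. A reader might infer a flat contradiction, and the text does not support that; it is an inconsistency the SAP leaves unresolved.

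A reader might also infer that baseline adjustment is impossible for the symptom day counts. It is not. Section 7.5 says baseline values, without requiring the same variable. A symptom score is assessed at V2, 8.2.1 already uses a baseline symptom score as a covariate, and rank-ANCOVA, one of the two listed options, accepts covariates. What is missing is the specification.

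Nor do the documents say that an unadjusted rank test is planned. They name no such test; they only fail to exclude one.

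Finally, these are secondary and exploratory endpoints of a trial the SAP itself calls exploratory, and the gain is small if r is high (92% against 94% power at r = 0.8). That is fair and limits the weight of the point. It does not justify leaving the model open when the covariates are already collected.

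**Conclusion.** The point holds as an inconsistency that permits a less precise analysis. Section 8.2.2.4 names the strata alone, 8.2.2.1 names no covariate and no single method, and 7.5 asks for both covariates everywhere, including for endpoints with no baseline of their own.

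For PROMIS, the illustrative size is an error variance with baseline of 0.65 to 0.90 of that without it. For the symptom day counts, it is a 16% to 49% reduction. Both rest on assumed correlations, and the PROMIS figures also on equal variances; the power figures further assume a 0.6 SD effect.

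It would be wrong to conclude that omitting baseline biases the comparison or invalidates the tests. Under randomization the cost is precision, together with chance imbalance left uncorrected in the trial at hand. The change is worth making before database lock, but it does not threaten the primary analysis.

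**What to change.** 1. **8.2.2.4 to 8.2.2.6, and the 8.2.3 measures that have a baseline:** specify ANCOVA, or rank-ANCOVA if the data are non-normal, adjusting for the baseline value of the same measure and the stratification factor.
2. **8.2.2.1 to 8.2.2.3:** specify rank-ANCOVA adjusting for the baseline total COVID-19 symptom score and the stratification factor, and delete the open non-parametric option.
3. **7.5:** limit baseline adjustment to endpoints with a baseline value or a named surrogate. State the covariates for 8.2.2.7 and 8.2.2.8 in those sections, because they would otherwise inherit the revised 8.2.2.1 by cross-reference.
4. **8.2.3, Global Health Assessment:** replace the change-from-baseline analysis with a comparison of the Day 56 values, since the questionnaire is completed only at V17.

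The cost is SAP wording only. The V2 PROMIS scores, the baseline symptom score and the stratum are already collected.
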